7.0 Study Procedures

7.1 Inclusion and Exclusion Criteria

Subject Inclusion and Exclusion Criteria - Subjects are required to meet all the inclusion/exclusion criteria to be eligible for participation (including intra-procedural criteria).

The following sections outline the specific inclusion and exclusion criteria for the study. Subjects who meet **all** of the general inclusion criteria and **none** of the exclusion criteria will be eligible for study participation.

Inclusion Criteria

To be eligible for enrollment in the study the following criteria must be met:

1. Subjects with paroxysmal atrial fibrillation who have had two or more spontaneously terminating episodes of atrial fibrillation that last longer than 30 seconds and shorter than 7 days, in the nine months prior to enrollment. At least one episode must be documented with ECG, transtelephonic monitoring (TTM), Holter monitor, or telemetry.
2. Failure of at least one Class I – IV anti-arrhythmic drug (AAD) for PAF as evidenced by recurrent symptomatic PAF, or intolerable side effects due to AAD. AADs are defined in **Appendix B**.
3. Signed informed consent.
4. Age 18 years or older.
5. Able and willing to comply with all pre-, post-, and follow-up testing and requirements.

Exclusion Criteria:

Subjects are **ineligible** for enrollment in the study if they meet **any** of the following criteria:

1. Atrial fibrillation secondary to electrolyte imbalance, thyroid disease, or reversible or non-cardiac cause.
2. Previous ablation for atrial fibrillation.
3. Atrial fibrillation episodes that last less than 7 days and are terminated by cardioversion.
4. Previous valvular cardiac surgery procedure.
5. Cardiac artery bypass graft procedure within the previous 180 days.
6. Previous septal defect repair.
7. Expecting cardiac transplantation or other cardiac surgery within the next 180 days.
8. Coronary PTCA/stenting within the previous 180 days.
9. Documented left atrial thrombus on ultrasound imaging (TEE).
10. Documented history of a thrombo-embolic event within the previous 365 days.
11. Diagnosed atrial myxoma.
12. Presence of an implanted ICD.
13. Presence of permanent pacing leads.
14. Significant restrictive, constrictive, or chronic obstructive pulmonary disease or any other disease or malfunction of the lungs or respiratory system with chronic symptoms.
15. Significant congenital anomaly or medical problem that in the opinion of the investigator would preclude enrollment in this study.
16. Women who are pregnant.

17. Acute illness or active infection at the time of index procedure documented by pain, fever, drainage, positive culture and/or leukocytosis (WBC > 11.000 mm³) for which antibiotics have been or will be prescribed.
18. Creatinine \geq 2.5 mg/dl (or \geq 221 μ mol/L).
19. Unstable angina.
20. Myocardial infarction within the previous 60 days.
21. Left ventricular ejection fraction less than 40%.
22. History of blood clotting or bleeding abnormalities.
23. Contraindication to anticoagulation.
24. Contraindication to computed tomography or magnetic resonance imaging procedures.
25. Life expectancy of less than 1 year.
26. Enrollment in another investigational study.
27. Uncontrolled heart failure (NYHA class III or IV heart failure).
28. Presence of an intramural thrombus, tumor, or other abnormality that precludes catheter introducing or positioning.
29. Presence of a condition that precludes vascular access.
30. Left atrial size \geq 50mm.
31. INR greater than 3.0 within 24 hours of procedure.*
32. Use of amiodarone therapy within the 3 months prior to the ablation procedure

**If subject's INR is minimally >3.0 within 24 hours pre-procedure, another INR may be done on day of procedure, if INR results < 3.0, subject may be enrolled.*

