2.2 Study Objective

To evaluate the safety and effectiveness of the family of Artisan guide catheters when used to remotely introduce and position specified commercially available cardiac RF ablation catheters to treat subjects with paroxysmal atrial fibrillation.

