Prior to the start of any ablation procedure, the subject's echocardiogram will be reviewed to ensure no evidence of left atrial thrombus. A routine EP study may be performed to evaluate the location, morphology, and dimensions of each pulmonary vein by venogram. Intra-cardiac echocardiography (ICE) may also be performed prior to the ablation procedure at the physician's discretion.

A subject is required to meet all the inclusion and none of the exclusion criteria to participate in the study. Enrollment occurs when a subject signs the Informed Consent Form. The subject must then meet all additional intra-procedural enrollment criteria (i.e. no intramural thrombus, etc.). If the subject does not meet all intra-procedural enrollment criteria, the subject will not be treated with the study device and will be withdrawn from the study. The screening, baseline, and withdrawal case report forms should be completed. The investigator shall report any acute procedural adverse events on the adverse event form.

These subjects who are withdrawn prior to the procedure will count against the maximum enrollment limit. However, the company requests that the maximum enrollment limit is increased accordingly to account for those who signed the Informed Consent Form but did not undergo the study procedure.

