6.7 Data Analysis

All statistical analyses will be done using the SAS software version 9.3 or later (Copyright © 2000 SAS Institute Inc., [name], USA. All rights reserved), R software or StatXact (Copyright © 2010, 1989-2012, Cytel Software Corporation).

All data will be collected as detailed in the clinical trial schedule. Subject demographics, medical history, risk factors, procedure characteristics, and outcome variables will be summarized using descriptive statistics for continuous variables (e.g. mean, standard deviation) and frequency tables or proportions for discrete variables.

The “Intention to Treat” (ITT) population includes all enrolled subjects. This includes subjects who signed an informed consent form. Subjects who are not enrolled due to not meeting the intra-procedural criteria are considered to be withdrawn from the study. Subjects who have already had a 14F introducer sheath introduced who subsequently are withdrawn during the procedure prior to treatment with the study device will be monitored for any acute adverse events related to the introduction of the 14F introducer sheath. Acute safety data for these subjects will be reported as a separate cohort, since these subjects are not treated with the study device. Additional subjects may be enrolled to replace subjects who were withdrawn due to not meeting the intra-procedural enrollment criteria. The primary statistical analysis will be performed on the cohort of subjects who are enrolled, meet the intra-procedural enrollment criteria, and are treated with the study device.

The following additional endpoints will be analyzed but will not be tested for statistical significance and will be reported as proportions, or means and standard deviations.

- Length of hospital stay,
- Total ablation time,
- Total ablation energy,
- Total fluoroscopy time,
- Total procedure time,
- Non-AF targets ablated manually,
- Ablative lesion sets in addition to those required for pulmonary vein isolation,

- Adverse events,
- Serious Adverse Events,
- Chronic success rates for subjects with a single procedure.

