- If subject meets any of the intra-operative exclusion criteria, withdraw the subject from the study. The screening, baseline, and withdrawal case report forms should be completed. Any acute procedural adverse events shall be reported on the adverse event form.

- The ablation catheter shall be inserted into the Artisan catheter. If the ablation catheter does not fit smoothly through the Artisan catheter, the poorly fitting catheter should not be used and should be replaced with another catheter.
- Ablation of the cavotricuspid isthmus may be performed only in subjects with a history of typical atrial flutter or inducible cavotricuspid isthmus dependent atrial flutter.
- SVC isolation shall be performed if AF triggering potentials are noted in the SVC.
- The ablation catheter will be remotely manipulated to map and ablate within the atria.
 - The ablation catheter shall be placed within the Artisan catheter and manually introduced into the subject under fluoroscopic guidance.
 - A CARTO or EnSite Velocity three-dimensional electroanatomic mapping system shall be used to map the anatomical locations of pulmonary veins and ablative lesions.
 - A circumferential anatomical approach shall be used to electrically isolate the pulmonary veins.

Recommended Ablation Parameters:

Place ablative lesions 1-2 cm outside of the pulmonary veins in order to minimize the risk of pulmonary vein stenosis. Target Sensei® IntelliSense readings of 10-20g, with a maximum of 40g, during lesion creation.

RF power should typically be set to 20-25W with a nominal maximum power of 30W. Starting at 20-25W in an anatomical region, RF power may be increased after 15 seconds in 5W increments to achieve a transmural lesion as shown by local atrial electrogram attenuation or splitting. Ablation duration at a single anatomical lesion location is recommended to be limited to 30 seconds. If the ablation output time for the RF generator is set for longer than 30 seconds, the ablation catheter should be moved so that the ablation duration in a particular location doesn't exceed 30 seconds.

When ablating on the posterior left atrial wall, power should be reduced to mitigate the occurrence of an atrio-esophageal fistula. RF power should typically be set to 15-20W, and should not exceed 20W. Esophageal temperature should be monitored and energy delivery should be terminated if the esophageal temperature reaches or exceeds 41°C, as measured from the esophageal temperature probe.

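### Open-ended intra-procedural criteria and an undefined treated cohort allow a failed attempt to introduce or position the Artisan to be left out of both primary tests

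*Protocol*

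**What the plan says.** Protocol 2.2 sets the objective as evaluating the Artisan family "when used to remotely introduce and position specified commercially available cardiac RF ablation catheters".

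Exclusion 28 in 7.1 removes subjects with "Presence of an intramural thrombus, tumor, or other abnormality that precludes catheter introducing or positioning". Section 7.1 notes that eligibility includes intra-procedural criteria but does not mark which ones they are. Section 5.0 says: "The subject must then meet all additional intra-procedural enrollment criteria (i.e. no intramural thrombus, etc". The one example given is an element of exclusion 28, and no list follows. A subject who fails is handled as follows: "the subject will not be treated with the study device and will be withdrawn from the study". Section 7.3.3 repeats the instruction: "If subject meets any of the intra-operative exclusion criteria, withdraw the subject from the study".

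Section 6.7 sets the analysis consequences:

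- Withdrawal can come after the 14F introducer sheath is in. The section provides for subjects "who subsequently are withdrawn during the procedure prior to treatment with the study device" and reports their acute safety data as a separate cohort.
- On replacement: "Additional subjects may be enrolled to replace subjects who were withdrawn due to not meeting the intra-procedural enrollment criteria".
- The intention-to-treat population is everyone who consented. The primary analysis is instead limited to enrolled subjects who meet the intra-procedural criteria and are treated with the study device. Treatment is not defined.

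The discontinued category in 15.0 covers subjects in whom the ablation catheter was inserted but no RF energy was applied. The reasons it gives are non-study equipment failure and a non-study arrhythmia.

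**The concern.** The residual clause of exclusion 28 describes a patient finding by its effect on introducing or positioning a catheter, and that is what the device is being tested for. With no closed list and no definition of treatment, the investigator chooses the label for a case in which the Artisan could not be brought into place: device failure, ineligible, or not treated. That choice can be made by someone who knows the attempt failed.

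The effectiveness denominator then loses subjects who would have been failures. On safety, vascular access complication is a component of the primary endpoint in 5.2, and 7.3.3 recommends a 14F sheath for introducing the Artisan. Complications of that access in withdrawn subjects nevertheless fall outside the 16% test. The trial is single-arm against fixed performance goals, so no control group is subject to the same selection.

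**Working it through.** **Step 1. Trace where an unpositioned Artisan can go.**

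| Rule | Where | Does it catch the case? |
|---|---|---|
| Acute failure if the Hansen system does not achieve isolation and manual completion is needed | 5.4, 6.4 | Only if the subject stays in the cohort and manual completion follows |
| Chronic failure if an AF target is ablated manually, or fewer than 3 of 4 veins are isolated | 5.3 | Only if the subject stays in the cohort |
| Discontinued | 15.0 | No: the reasons given do not include study-device failure |
| Withdrawn on an intra-procedural criterion | 5.0, 7.3.3, 6.7 | Can be used, through the residual clause of exclusion 28 |
| Not treated with the study device | 6.7 | Can be used, because treatment is undefined |

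**Step 2. Reproduce the plan's own figure.** Inputs from 6.1, 6.2 and 6.5: goals of 16% and 54%, posterior probability of at least 0.95 for each, assumed true rates of 8% and 72%, and 125 to 250 subjects. Assumptions: flat Beta(1,1) priors and independent endpoints, because Appendix M is not shown.

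- n = 250: success needs at least 148 effectiveness successes and at most 30 safety events. Power is 1.0000 × 0.9897 = 0.990.
- n = 125: the cut-offs are 77 and 13. Power is 0.9955 × 0.8737 = 0.870.
- A simplified adaptive simulation (accrual assumed at 3, 5 or 8 per month, futility cut-off off or 0.05) gives 0.981 to 0.989.

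The stated 98% is reproduced. The figure is sound, and the question is which subjects it describes.

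**Step 3. Size of the effect.** Let f be the share of attempted subjects left out because the Artisan could not be introduced or positioned. The documents give no value for f, so it is assumed. Each such subject is taken to be an effectiveness failure and to be replaced, so n is unchanged.

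If the true rate among all attempted is 54%, the analysed rate is 0.54 / (1 − f). The chance of passing is the exact binomial tail at the cut-off in step 2, with a single look at effectiveness alone.

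| f | Analysed rate | P(pass), n = 250 | P(pass), n = 125 |
|---|---|---|---|
| 0 (all counted) | 0.5400 | 0.056 | 0.053 |
| 1% | 0.54/0.99 = 0.5455 | 0.078 | 0.067 |
| 2% | 0.54/0.98 = 0.5510 | 0.107 | 0.085 |
| 3% | 0.54/0.97 = 0.5567 | 0.145 | 0.106 |
| 5% | 0.54/0.95 = 0.5684 | 0.246 | 0.163 |

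**Step 4. What counting them would cost a good device.** If 72% holds among treated subjects, the rate among all attempted is 0.72 × (1 − f).

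| f | Rate among attempted | Effectiveness power, n = 250 | Effectiveness power, n = 125 |
|---|---|---|---|
| 1% | 0.7128 | 1.000 | 0.993 |
| 2% | 0.7056 | 1.000 | 0.988 |
| 3% | 0.6984 | 0.9999 | 0.981 |
| 5% | 0.6840 | 0.999 | 0.957 |

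At f = 0 the values are 1.000 and 0.9955.

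**Step 5. Safety.** No rate of access complications in withdrawn subjects is given, so no probability is computed. For scale, the limits in step 2 are 30 events at n = 250 and 13 at n = 125.

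**The case against.** A reader might infer that exclusions 28 and 29 make inability to introduce or position the catheter an eligibility failure in itself. The text does not say so. Both require an abnormality or condition in the patient, and the residual clause follows thrombus and tumor, so it is naturally read as the same kind of finding. Exclusion 29, "Presence of a condition that precludes vascular access", is never named as intra-procedural, and any catheter ablation needs vascular access. This stands.

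The sequence in 7.3.3 also helps the plan. The withdrawal instruction is listed after the baseline echocardiogram and before the ablation catheter goes into the Artisan and is introduced and steered. Read as a strict order, there is no positioning result yet at that step. This narrows the opening. It does not close it, because no sentence makes that step the last point for withdrawal, and 6.7 puts the limit only at treatment with the study device, which is undefined.

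Failure rules exist in 5.3, 5.4 and 6.4, so it would be wrong to say that the plan ignores device failure. They apply only to subjects who remain in the cohort.

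There are other safeguards: withdrawal and adverse event forms, a defined intention-to-treat population, a screening log and 100% monitoring. They make such cases visible without putting them into the primary tests. Further analyses may sit in Appendix M or a statistical analysis plan, but the primary population is fixed in protocol 6.7.

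On size, it is tempting to use the 5% in 6.5 as the rate of hidden failures. That figure covers all reasons and refers to withdrawal before the procedure, with enrollment counted from consent. Table 1 shows 100% acute success in the Hansen arms, as each study defined it, and 9.1 requires at least 20 Hansen procedures in the past 12 months. Both suggest that the true rate may be low.

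**Conclusion.** The gap is real, but it is a matter of what the text permits. It does not show that device failures will be removed. An open clause, unlisted criteria and an undefined term together allow an attempt that failed for device reasons to leave both primary tests, and possibly to be replaced. Complications of the 14F access in withdrawn subjects are reported only separately. A reader might conclude that the protocol directs such failures to be withdrawn, or that a particular inflation of the false-pass rate is established. The documents support neither.

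The range of about 8% to 25%, against 5.6%, rests on assumed omission of 1% to 5%, a true rate exactly at the goal, every omitted subject being a failure, 250 analysed subjects, a flat prior and one look. The interim analyses and the joint safety requirement are ignored. At the planned 72%, effectiveness power at 250 subjects stays at 99.9% or more over the same range. At 125 subjects it falls from 99.6% to 95.7% at most. The change should be made, because it removes a selection that could depend on the outcome and costs an effective device little.

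**What to change.** - **7.1 and 7.3.3.** List the intra-procedural criteria as a closed set of device-independent findings, such as thrombus, tumor or another structural abnormality. Require them to be established by imaging or examination no later than the baseline echocardiogram and before introduction of the Artisan is attempted. The cut-off should not be sheath insertion, because 7.3.3 lists the required baseline echocardiogram after introducer insertion and trans-septal puncture.
- **6.7, cohort.** Define treatment with the study device as attempted introduction of the Artisan. From that point, a subject in whom it cannot be introduced or positioned stays in the primary cohort, counts as an acute and a chronic failure, and has complications counted in primary safety.
- **6.7, safety.** For subjects withdrawn after 14F sheath insertion but before any Artisan attempt, keep the separate report and add a sensitivity analysis of the 16% test that includes them.

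The cost is wording, with no added tests or visits. The change concerns how cases are classified for analysis. It does not bear on whether an operator should continue a procedure. The reported success rate may be slightly less favourable, and a patient whose anatomical barrier is first found during the attempt will count as a failure.

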7.2 Assignment of Subject Identification Number

All subjects screened and enrolled in the study will be assigned a subject ID number. The format is alpha numeric and three parts. The first part represents the three character site identifier (assigned by Hansen Medical) consisting of two digits followed by the letter "A", i.e., 01A, 02A, etc. The second part is numeric (three digits), assigned sequentially beginning with 001 for the first subject. The third part consists of the subject's initials. Thus, the first subject, Mickey Sue Mouse at site 01 will be assigned 01A-001-MSM; the next subject, Donald Duck (no middle name), will be assigned an identification number of 01A-002-D-D, etc. Per regulations, we cannot collect subject initials for all of the OUS sites participating in this study, therefore we will use "OUS" for all OUS subject initials. The subject initials for OUS sites will be: site identifier (assigned by Hansen Medical) – identifying sequential number- OUS.

7.3 Baseline, Pre-Procedure, Procedure, Pre-Discharge and Follow-up

The definition of study time points and schedule of study assessments to take place during the study are outlined in Table 8 and Table 9 below. The events and assessments that are to

take place at each study time point are described in detail below. Standard of care for events and assessments may vary from site to site.

7.3.1 Screening/Baseline Evaluation – within 30 days of enrollment

The following baseline data must be collected from all subjects prior to enrollment in the study. Subjects will be screened for eligibility by the investigator or designee. Subjects who meet the eligibility criteria for participation will be required to read and sign an Informed Consent Form prior to baseline evaluation. A medical history inclusive of medications will be taken and a physical examination will be performed to assess overall physical status.

Test results that are within the timeframes specified below may be used even though the actual test was done prior to the subject's informed consent. This may be done only for standard of care tests with the intent to minimize stress and discomfort to the subject and reduce costs. Required screening evaluations include the following.

The following evaluations will be conducted at the baseline visit:

- Inclusion/Exclusion criteria assessment,
- Informed consent,
- Demographics,
- Medical history,
- Medication history: Antiarrhythmics (2 years); Anti-platelets & Anticoagulation (3 months),
- Physical examination,
 - Vital signs,
 - New York Heart Association (NYHA) Class (see **Appendix E**),
- Laboratory evaluations,
 - CBC,
 - INR (only if subject previously on anticoagulation therapy),
 - Serum Creatinine,
 - Blood Urea Nitrogen (BUN),
 - Pregnancy test (women of child bearing potential) – ***within 7 days of procedure***,
 - If a subject become pregnant during this study, she must notify the site staff
- TTE to assess cardiac structure, function, LA size and EF (***within 3 months prior to procedure***),
- ***CT or MR (within 3 months prior to procedure)*** to evaluate pulmonary vein and left atrial morphology and dimensions.

Note: If a CT or MR is performed at baseline, the same imaging specifications performed at baseline must be performed at the follow-up visit for 180 and 365 day.

7.3.2 Pre-Procedure Evaluation – Within 24 hours of procedure

Within 24 hours prior to the initial ablation the following will be done:

- Blood will be drawn to measure for INR value*,
- 12-lead electrocardiogram (ECG) performed to check for cardiac rhythm and indication of myocardial ischemia,
- TEE/ICE should be performed to assess for possible atrial thrombus 24 hours prior to procedure or the day of the procedure. Also to establish that thrombus, cardiac structure, function, LA size and EF meet protocol criteria.

**If subject's INR is minimally >3.0 within 24 hours pre-procedure, another INR may be done on day of procedure, if INR results < 3.0, subject may be enrolled.*

Table 8: Definition of Study Time Points

Interval	Time Point and Window (if applicable)
Screening/Baseline	Within 30 days except for pregnancy test (within 7 days), from initial ablation
Pre-procedure	Within 24 hours prior to the initial ablation.
Enrollment	Subject is considered to be enrolled once they sign the Informed Consent Form.
Discharge	0 – 48 hours or prior to discharge; whichever comes first.
7-Day Follow-up	7 days \pm 3 days.
30-Day Follow-up	30 days \pm 14 days post initial ablation procedure.
90-Day Follow-up	90 days \pm 14 days post initial ablation procedure.
180- Day Follow-up	180 days (6 months) \pm 30 days post initial ablation procedure.
365- Day Follow-up	365 days \pm 30 days post initial ablation procedure.

